5.0 Study Procedures

This iterative design process requires multiple cohorts until reaching the general agreement in terms of participants' satisfaction and feedback on the intervention. Below is the steps to iterative process of developing Sit Less Program.

As of today (May 15, 2023), we are currently undergoing the first phase, testing Sit Less V1 and will collect participants' feedback in June 2023. We also collected user's feedback from a sibling study " Reducing sedentary time in patients with cardiovascular disease: A pilot randomized controlled trial (Sit Less Study)" IRB # 220416. This sibling study has the same intervention components and is now undergoing qualitative analysis based on intervention group participants' feedback.

35

Below is a detailed study process over time for all of cohort participants.

5.1. Baseline visit 1: Initial contact, screening, and consent

Interested respondents will be screened by a trained research staff over the phone or in-

person, depending on the recruitment methods. For this research, no aspect of the participant's diabetes treatment regimen will be modified.

Those who are eligible for the study will be invited to the in-person visit. The first visit (i.e. Baseline visit 1) will be conducted at VUSN (Vanderbilt School of Nursing)'s lab at Wesley building.

At the Baseline visit 1, the trained research staff will ask the individual what their most recent blood glucose level was. If their reported glucose levels are between 80-300, they will complete the informed consent with assistance from the trained research staff.

Those who are consented will participate in 1) completing survey questionnaires (30minutes), 2) biometric assessments 3) brief instruction regarding the wear of activPAL and continuous glucose monitoring (CGM) devices (30 minutes), and 4) start to wear two devices for 7 days. The activPAL3 device (PAL Technologies Ltd., Scotland, UK) will be worn on the thigh and a CGM (Abbott FreeStyle Libre) will be attached to the upper arm. The research staff will provide 1) a copy of the informed consent form; 2) instructions with photos and 5 waterproof dressings (Tegaderm) for attaching the activPAL on the thigh; 3) information about the CGM; and 4) daily sleep diary and wear log for 7 days. Participants will receive \$25 for baseline visit 1.

1. Questionnaires

Participants will be given an iPad to answer questions about their demographics, socioeconomic characteristics, and a series of questionnaires detailed below. All responses will be recorded in REDCap.

- a) **Demographics:** demographics and socio-economic status will be self-reported by the patients.
- b) **Health behavior:** Questions about their tobacco use, alcohol intake, physical

activity (measured using the 16-item Global physical activity questionnaire²¹), sedentary behavior (measured using 11-item Weekly sitting inventory²²), and diet (measured using the 16-item Rapid Eating and Activity Assessment for Participants Short Version (REAP-S)²³, sleep quality (measured using the 10-item Pittsburgh sleep quality index²⁴) will be answered with the assistance of the study team member.

c) **Confidence in reducing SB and increasing PA:** Confidence in reducing SB and increasing physical activity will be measured using 12 items from the Self-

Efficacy Questionnaire for Physical Activity and Sedentary Behavior (Cronbach's alpha = 0.79).²⁵

- d) **Habit strength for SB:** Habit strength for SB will be assessed by using a validated measure, Self-Report Habit Index (Cronbach's alpha = 0.91).²⁶ This 7-item index was adapted to sedentary breaks (standing/walking) to assess the degree to which sedentary breaks become habitual.
- e) **Quality of life:** Quality of life will be measured by using the 12-item Short Form Health Survey (SF-12). The SF-12 is well-validated in T2D patients²⁷ and provides physical and mental health scores.²⁸
- f) **Medical history and current medication:** Medical history and current medication will be self-reported by the patients.
- g) **Depressive symptoms:** Depressive symptoms will be measured by using Patients Health Questionnaire 9 (PHQ-9)²⁹.
- h) **Diabetes self-management:** Self-efficacy of diabetes self-management will be measured by the Perceived Diabetes Self-Management Scale³⁰.

2. Biometric assessments

Participants will undergo a basic physical examination (e.g., height, weight, blood pressure, hip circumference, waist circumference).

- a) **Anthropometrics:** Height, weight, and waist and hip circumferences will be measured using a validated stadiometer, digital scale, and flexible tape measure, respectively. All measurements will be recorded to the nearest 0.1 cm and 0.1 kg.
- b) **Blood pressure:** Blood pressure will be measured using an automated and validated BP monitor. In a private room, participants will be seated comfortably for 5 minutes with feet flat on the ground prior to measurements.³² The device will take three readings at 2-minute intervals and the mean of three BP readings will be recorded.³²
- c) **Random glucose via finger prick:** The trained research staff will conduct a finger prick and one drop of blood will be obtained on a glucometer. The glucometer will be used to test their random glucose. Participants will NOT be required to fast overnight prior to the study visit. If the random glucose >300, the PI will be immediately informed and the participant will be withdrawn per the protocol (see section 7).

3. ActivPAL

The activPAL is a non-invasive method of monitoring activity and rest cycles through an inclinometer. The device will be worn on the anterior upper thigh of the dominant leg and kept in place by an adhesive pad (Tegaderm). If the participants have hair on the upper thigh, shaving an area of the thigh will be considered; we will provide a disposable shaving razor and foam as well as a private room with a sink. The participant will apply the device by themselves in a private room. The participants will wear the activPAL 24hours over a 7-day period. There is no need to charge the device. The activPAL monitor has been validated against direct observation and is the most sensitive device to detect sitting-to-standing transitions.³¹ At a follow-up visit (Baseline visit 2), the activPAL data will be downloaded to the secured PI's computer and summary reports will be reviewed by the study team member and the participants.

4. Continuous Glucose Monitor (CGM)

The device (FreeStyle Libre Pro™; Abbott Diabetes Care, Witney, Oxon, UK) will be worn on the back of the upper arm to measure their 24-hours glucose levels for 7

days. The CGM has one sensor applicator, one sensor, and one reader. Skin will be prepared using an alcohol wipe and the sensor applicator will be placed over the application site. The research staff will press firmly, hold for a few seconds, and gently pull the sensor applicator away from the site. A sensor applicator has an introducer needle which will be retracted after application. Only a thin, flexible filament will remain under the skin and the sensor is held in place by an adhesive. The sensor applicator serves as a container for disposal. The water-proof sensor, worn on the upper arm, is factory calibrated. The reader is retained by the PI and data are not visible to participants during sensor wear. The sensor automatically captures and stores glucose data every 15 min (96 glucosereadings/day).

5. Sleep diary and wear log

The participants will be asked to complete a daily sleep diary each morning while they are wearing the monitor, which takes about 2 minutes. The participant will also complete a daily wear log each evening. The information about sleep onset and offset and wear time will be used to validate the activPAL wearing protocol.

Once they complete the 7 days of activPAL and CGM monitoring, they will be scheduled for the in-person visit (Baseline visit 2) and will return the devices and log to the study team at the visit.

5.2. Baseline visit 2

5.2.1. Device removal

The in-person baseline visit 2 will take place at the VUSN Clinic in the Wesley building. Participants will return the activPAL and the continuous glucose monitoring devices at Baseline visit 2. The trained research staff will assist the participant in removing the two devices as needed, and then download the data from the activPAL and CGM devices. Baseline visit 2 will last approximately 1 hour and 30 minutes. Participants will receive \$25 for baseline visit 2.

1. ActivPAL data download

The 7 days of activPAL data will be downloaded and stored in the secured PI's computer. The variables of interest from the activPAL data are listed below:

- a) **Sedentary behavior:** SB will be objectively measured as time spent sedentary (sitting or lying, minutes/day) and number of prolonged sedentary bouts (>30 minutes and >60 minutes) using the activPAL3. ActivPAL data will be downloaded and processed using activPAL software.
- b) **Physical activity:** Time spent standing and walking (stepping), number of sitting-to-standing transitions, and daily step counts will be measured using the activPAL.

2. Continuous glucose monitoring data download

The 7 days of CGM data will be downloaded via Libreview and stored in the PI's computer. The variables of interest from the CGM data are listed below:

- a) The 24-hour glucose control: the 24-hour glucose control will be evaluated by mean 24-hour glucose levels and numbers of events and time in hypoglycaemia (glucose < 3.9 mmol/l), euglycaemia (glucose 3.9–7.8 mmol/l), hyperglycaemia (glucose > 7.8 mmol/l) and above target (glucose > 9 mmol/l).

5.3. Intervention

The 8-week intervention will consist of four components. All study subjects will be assigned to intervention group. After the intervention, the study subjects will keep their Fitbit and the HidrateSpark smart water bottle.

5.3.1. Instructional/goal setting session

The study team member will provide an orientation at the baseline visit 2. The study team member will review the activPAL data and identify targetable prolonged SB bouts. The study team member and the participant will set two goals: 1) a SB reduction goal will be set as reducing daily sedentary time gradually until they reach the goal of ≥ 120 minutes SB reduction; and 2) a sedentary break goal will be set as 3 minutes of standing/walking every 1 hour and then increasing its duration to 5 minutes and its frequency to every 30 minutes. These goals were feasible in stroke patients and T2D patients.^{16,33} The participant will enter the goal into the Fitbit for self-monitoring and fill out the first worksheet in the Ten Top Tips (TTT). The TTT is a booklet developed from the Habit Formation Theory and includes 10 tips to add SB breaks into their daily routine.³⁴ The ten tips are modified to eight in our study. See Appendix for the TTT and worksheet. This goal session will last 1 hour.

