SB breaks can be achieved through self-monitoring and prompts from a wearable device. In addition, the use of a smart water bottle may be a promising strategy to naturally break sedentary time due to the impact of increased water intake on kitchen and restroom breaks. A smart water bottle can sync with an activity tracker, which could synergistically motivate the T2D patients to reduce SB. This new technique is a potentially low-cost and sustainable strategy to deliver SB reduction interventions. Because there is no SB reduction program specifically focusing on sedentary breaks in T2D patients, we propose to develop and conduct a pilot study to test a wearable technology-based SB reduction intervention in T2D patient. The 8-week intervention includes: 1) one instructional and goal setting session; 2) the use of a wearable device (Fitbit) that provides stand/walk prompts and self-monitoring; 3) a smart water bottle (HidrateSpark) that syncs with the Fitbit, and 4) weekly tailored text messages for behavior reinforcement and weekly goal monitoring. Since text messages and wearable device-based intervention requires a complex and multiple iterative process to customize research participants' needs and refine the contents and frequency of the text messages. To find the most suitable frequency and contents of text messages, we will use an iterative design process. Outcomes will be measured at baseline and post-intervention. Specifically, we aim to: **Aim 1:** Determine the feasibility and acceptability of the SB reduction intervention in T2D patients by evaluating reach, retention, satisfaction, and compliance with the

intervention.

Aim 2: Evaluate the preliminary efficacy of the SB reduction intervention on changes in total SB time and numbers of prolonged SB bouts.

Aim 3 (Exploratory Aim): Explore preliminary effects of the SB reduction intervention on light physical activity (total standing and stepping times), cardiometabolic markers (24-hour glycemic control, BMI, waist circumference, blood pressure) and patient-centered outcomes (confidence in reducing SB, habit strength for SB, and quality of life).

3. Inclusion/Exclusion Criteria

Inclusion criteria: 1) ages 18 and above, 2) diagnosed with type 2 diabetes, 3) self-reported HbA1C<13, 4) self-report of sitting \geq 8hr/day, 5) ability to stand and walk, 6) ownership of a smartphone.

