5.4. Post-intervention visit

After 8 weeks, all participants will be invited to an in-person visit (post-intervention visit). During the visit, all the above parameters will be re-measured by the same trained research staff. The visit will take approximately 1 hour including completion of a series of questionnaires (which may be completed by the participants beforehand) and biometric assessments. All participants will wear the activPAL3 and the CGM for 7 days to examine their post-intervention activity and glycemic control. They will return the devices via pre-paid mail. All participants will receive \$50 for the post intervention visit, and an additional \$50 for mailing back the devices to the study team.

Therefore, total compensation would be \$150 for each participant. Also, all participants will be informed of their 24-hour glucose results, and activity patterns retrieved from the ActivPAL device. A subsample of participants from the intervention group will be invited to participate in a separate qualitative exit interview. The one-on-one exit interview will be conducted by the trained study team member during the visit. The interview will last 30 minutes, and each participant will be compensated with \$30 for completing this interview.

1. Questionnaires

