The activPAL activity tracker is a safe, non-invasive method to capture information about activity cycles. Participation in this study requires that participants wear an activPAL tracker taped (using Tegaderm adhesive dressing) to the front of the right thigh during waking hours for a minimum of 7 consecutive days (baseline and follow-up). The Tegaderm adhesive dressing used to apply the activPAL devices are hypoallergenic and consist of a dual layer hydrogel that does not pull at the skin or hair. There are few risks associated with wearing the activPAL device and include slight discomfort, such as light pressure from the activPAL or irritation from the waterproof dressing.

Continuous Glucose Monitor

The FreeStyle Libre Pro Flash Glucose Monitoring System is an FDA-approved, professional continuous glucose monitoring device indicated for detecting trends and tracking patterns in persons (age 18 and older) with diabetes. After application of the sensor, only a thin, flexible filament will remain under the skin and the sensor is held in place by an adhesive. The following are possible adverse effects of inserting a sensor and wearing the adhesive patch: local erythema (redness), local infection, inflammation, pain or discomfort, bleeding at the glucose sensor insertion site, bruising, itching, scarring or skin discoloration, and adhesive irritation. There is a remote risk of sensor or needle fracture during insertion, wear or removal, with fragments retained under the skin.

Fitbit

Vanderbilt Diabetes and Research Training Center, P&F DK020593

Participants will wear an additional wrist-worn activity tracker for 8 weeks during waking

hours. There are few risks associated with wearing the device and include slight discomfort, such as light pressure from the wristband or irritation from wearing a damp band after showering or swimming. There is a possible risk of confidentiality loss. To reduce the risk, we will create an anonymous email account for the Fitbit app. All identifiable data will be kept on password-protected computer systems in a locked office.

Smart Water bottle

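### activPAL wear is 24-hour in section 5.1 but waking-hour in section 6.0, and no rule removes sleep from the Aim 2 sedentary time and bout counts

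*Combined protocol and SAP*

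**What the plan says.** - **Goal.** Section 5.3.1 works in daily minutes: "a SB reduction goal will be set as reducing daily sedentary time gradually until they reach the goal of" a cut of at least 120 minutes.
- **Outcome.** Aim 2 (section 2.0) concerns "changes in total SB time and numbers of prolonged SB bouts". Section 5.2.1 measures these on the activPAL as "time spent sedentary (sitting or lying, minutes/day) and number of prolonged sedentary bouts (>30 minutes and >60 minutes"). It sets no waking-hours limit and gives no settings for the activPAL software.
- **Wear, section 5.1 (ActivPAL).** "The participants will wear the activPAL 24hours over a 7-day period", on the dominant leg.
- **Wear, section 6.0 (ActivPAL).** The device is taped to the right thigh "during waking hours for a minimum of 7 consecutive days", for both baseline and follow-up.
- **Wear, section 5.4.** The post-intervention week is seven days; the hours of wear are not stated.
- **Sleep diary and wear log, section 5.1.** "The information about sleep onset and offset and wear time will be used to validate the activPAL wearing protocol". No other use is given there or in section 8.0.
- **Return of materials.** At baseline, participants "will return the devices and log to the study team at the visit". After the intervention, section 5.4 says "They will return the devices via pre-paid mail" and does not name the diary or log.
- **Water component.** Sections 2.0 and 6.0 present the bottle as a way to break up sitting through kitchen and restroom trips. Section 5.3.3 advises 4.5-6 bottles of 500 ml a day.

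**The concern.** The two wear instructions cannot both be followed, and the outcome definition does not settle which hours count. A 24-hour record scored as section 5.2.1 is written counts the night as sedentary minutes and as at least one bout over 60 minutes. A waking-hour record leaves the night out. Both results would carry the same outcome name.

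Two things follow for Aim 2. First, if a participant, or the staff instructing them, follows one section in the baseline week and the other in the post-intervention week, the difference in nights counted appears as a change in sitting. Second, the bout count is exposed through the intervention itself. Extra water may mean extra trips at night, and in a 24-hour record each trip cuts one long lying period into two. That can raise a count that the programme is meant to lower. Section 8.0 plans effect-size estimates for these outcomes, so the scoring rule carries through to what the pilot reports.

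**Working it through.** **1. The plan's own figure.** Section 8.0 gives 16 recruited, cohorts of 10, 15% attrition, 24 more and 40 in total. Two remaining cohorts (my reading; the number is not stated) give 20 / 0.85 = 23.5, rounded up to 24, and 16 + 24 = 40. The figure reproduces and does not depend on how sedentary time is defined.

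**2. When the total is and is not biased.** Write a day's recorded total as W + S, where W is waking sedentary minutes and S is sleep minutes counted.
- Full 24-hour wear in both weeks: change = (W2 - W1) + (S2 - S1). With stable sleep, S2 = S1 and the change is W2 - W1. No bias.
- Waking-hour wear in both weeks, with no sleep recorded: S1 = S2 = 0. The change is again W2 - W1.
- Mixed wear: nights counted in one week only do not cancel.

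**3. Size under mixed wear.** Sleep length is not in the documents; I assume 6-9 hours, or 360-540 minutes. If k of 7 nights are counted in one week and not in the other, that person's 7-day mean shifts by k x S / 7.

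| Nights counted in one week only | 6 h sleep | 9 h sleep |
|---|---|---|
| 1 | 360 / 7 = 51 min/day | 540 / 7 = 77 min/day |
| 2 | 720 / 7 = 103 min/day | 1080 / 7 = 154 min/day |

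Nights counted only at baseline look like a reduction in sitting; nights counted only afterwards look like an increase. For scale, the participant goal is 120 minutes. The group mean moves by the average of these shifts across participants, so scattered lapses mainly add noise, while lapses in one direction add bias.

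**4. Bout counts under 24-hour wear.** Assume a 7-hour night (420 minutes) and k evenly spaced trips, ignoring the time each trip takes. The night gives k + 1 bouts of 420 / (k + 1) minutes. At k = 5 each lasts 420 / 6 = 70 minutes, still over 60. So each extra trip, up to five, adds one bout to both the over-30 and the over-60 count for that day. With sleep excluded it adds none. Uneven spacing can make the increase smaller: a trip soon after lying down leaves one piece too short to count.

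**The case against.** The best defence is that the documents point towards a waking measure. Section 1.0 describes sedentary behaviour as a share of waking time, section 5.1 collects sleep onset and offset every day, and section 5.1 is the operative procedure while section 6.0 is risk text. The data needed for a sleep rule are therefore planned. This stands, and it is why the repair is small. It does not supply the rule: the diary's one stated use is to validate wear, and the outcome definition covers all sitting or lying.

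It can also be said that this is an exploratory pilot with descriptive models and no decision threshold on sedentary time. That is right and limits the consequence.

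Several stronger readings are tempting, but the documents do not support them.
- *The 120-minute goal has no reference point.* A reduction agreed in the session where the baseline activPAL week is reviewed is ordinarily read as a reduction from baseline. The appendix worksheets and message examples are not in the copy reviewed, so silence cannot be shown.
- *A goal taken from a 24-hour total would already be met on the Fitbit.* Section 5.3.1 sets a reduction, not a level carried between devices, and section 5.3.4 bases weekly feedback on Fitbit data.
- *The two scoring rules give opposite answers.* That requires a systematic change in time in bed. Assuming an extra hour in bed yields a 60-minute gap by construction, and nothing in the plan suggests such a change.
- *The diary is not kept after the intervention.* Section 5.4 says that the earlier measurements are repeated, and section 5.1 ties the diary to wearing the monitor. Only its return by mail is left unnamed.

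**Conclusion.** The concern holds in a limited form. The wear instructions conflict on both hours and leg, and the stated Aim 2 outcomes, applied literally to a 24-hour record, count sleep as sedentary time and as prolonged bouts. The change in total time is biased only if the nights counted, or sleep itself, differ between the two weeks. On an assumed 6-9 hours of sleep, one such night shifts a participant's mean by about 51-77 min/day. The bout count is exposed even with full wear if the water component adds night-time trips; how often that happens is not known from the documents. A reader might infer that the Aim 2 change in total sitting is unreliable whatever happens. It is not: with stable sleep and full 24-hour wear in both weeks, sleep cancels. The sample size is unaffected. This is a point to consider and correct, not one that undermines the pilot.

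**What to change.** 1. Keep 24-hour wear as in section 5.1, and correct the ActivPAL text in section 6.0 (hours and leg) to match. Repeat the 24-hour instruction in section 5.4.
2. In section 5.2.1, exclude the diary-recorded sleep period from total sedentary time and from both bout counts, at baseline and post-intervention. State the handling of a missing diary night, for example that person's mean times in the same week. A night not worn then no longer shifts the total, provided the gap lies within the sleep period.
3. In section 5.4, name the sleep diary and wear log among the items mailed back.
4. Report the 24-hour total as a sensitivity result. Sedentary time as a share of waking time may be added as a supplement; it need not replace minutes per day, since that would change what is estimated.

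The cost is wording in sections 5.2.1, 5.4 and 6.0, plus two existing forms in the mail pack, with no new device, visit or participants. Records already collected can be reprocessed where diaries were kept; post-intervention diaries that were never returned cannot be recovered, so the change is best made before the remaining cohorts finish. The downside is that diary errors will move some minutes across the sleep boundary.
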